4 STUDY DESIGN

4.1 OVERALL DESIGN

We will enroll up to N=20 adults (aged 18-70 years) with TRD, defined as inadequate improvement with two or more antidepressants in the current episode. If patients are on antidepressant medications, they must be on a stable dose for >4 weeks prior to treatment. Patients will not be on any medication or nutritional supplement known to affect inflammatory status. Primary inflammatory disorder or an unstable medical condition will also be exclusionary. Subjects will receive 3 doses (160 mg at week 0, 80 mg at week 2, 80 mg at week 4) in total of ixekizumab injection, with dosing to occur every 2 weeks over a 6-week period. The primary clinical outcome will be safety and feasibility of ixekizumab as treatment for patients with TRD. The secondary clinical outcome will be change in MADRS from baseline to week 6, additional clinical outcomes, and changes in immune markers in the blood. Participants will undergo neuroimaging with DCE-MRI and rs-fMRI at baseline and at the primary outcome visit to measure the effect of treatment and change in depression severity on BBB permeability and reward circuit function.

4.2 SCIENTIFIC RATIONALE FOR STUDY DESIGN

We have selected to use an open-label study design for this study to determine the impact of ixekizumab in adults with TRD and no history of primary immune disorders. If successful, data from this study will be used to inform the design of larger randomized controlled clinical trials to further test the stated hypotheses.

4.3 JUSTIFICATION FOR DOSE

The use of ixekizumab via subcutaneous route is consistent with the FDA-approved usage for other indications (psoriasis). The dosing regimen is based on the report by Griffiths et al.¹⁶ which evaluated the impact of ixekizumab on depressive symptoms in three Phase 3 trials. In their report, which included

patients with psoriasis and moderate-to-severe depression, ixekizumab was started at 160 mg. Over the next 12 weeks, patients either received 80 mg of ixekizumab every 2 weeks (Q2W), 80 mg of ixekizumab every 4 weeks (Q4W), or placebo. Remission from depressive symptoms was more common in those who received ixekizumab Q2W (45.2%) as compared to ixekizumab Q4W (33.6%) or placebo (17.8%). Therefore, our planned use of ixekizumab with dose of 160 mg at baseline, and 80 mg at weeks 2 and 4 at a Q2W dosing interval is consistent with the dosing regimen found to be most effective in attaining remission of depressive symptoms in the Phase 3 clinical trials of patients with psoriasis and moderate-to-severe depression.

4.4 END OF STUDY DEFINITION

A participant is considered to have completed the study if he or she has completed all phases of the study including the last visit or the last scheduled procedure shown in the Schedule of Activities (SoA), Section 1.3. Alternatively, a participant may be considered exited from the study due to early withdrawal, drop-out, or screen failure. See Section 7 for more details.

5 STUDY POPULATION

5.1 INCLUSION CRITERIA

1. Written informed consent (and assent when applicable) obtained from subject;
2. Ability for subject to comply with the requirements of the study as determined by the PI;
3. Men and women, age 18-70 years;
4. Participants must meet DSM-5 criteria for Major Depressive Disorder [MDD]) in a current major depressive episode (MDE) as determined by a study psychiatrist and confirmed using the Structured Clinical Interview for DSM-5 Research Version (SCID-5-RV);
5. Participants have had ≥ 2 adequate trials of antidepressants/augmentation strategies during current episode. (Refer to ATRQ Guidelines for Completion for guidelines on dose/duration required for a trial to be considered adequate.);
6. If patient is on antidepressant medication, they must be on a stable dose for >4 weeks prior to treatment;
7. Quick Inventory of Depressive Symptoms – Clinician Administered (QIDS-C) score ≥ 14
8. If female of childbearing potential, must agree to use of a medically accepted form of contraception, or else agree to abstinence until 6 months after the last dose of study drug.
9. Male patients, if heterosexually active with a partner who is female of childbearing potential, pregnant, or breastfeeding, must agree to barrier contraception for the treatment period and for at least 6 months after the last dose of study drug. Female partners of male participants must use at least one form of highly effective contraception starting at least one cycle prior to male patient study drug initiation until 6 months after the last dose of study drug.

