Secondary Endpoints: 1) Baseline-to-week-6 changes in depression severity as assessed by MADRS score; 2) Response and remission rates at week 6 (defined by $\geq 50\%$ MADRS total score improvement and MADRS total score of ≤ 10 , respectively); 3) Measures of global illness [Clinical Global Impression Severity (CGI-S) and Improvement (CGI-I) scale], overall depression [the Quick Inventory of Depressive Symptomatology Self-Report (QIDS-SR)], anxiety [Hamilton Anxiety Rating Scale (HAM-A)], suicidal ideation and attempt [the Columbia Suicide Severity Rating Scale (C-SSRS)], anhedonia [the Snaith Hamilton Pleasure Scale (SHAPS) and the Temporal Experience of Pleasure Scale (TEPS)], and symptoms associated with depression such as fatigue, sleep/wakefulness disturbances, anxiety, and irritability; 4) Baseline-to-week-6 changes in blood-based immune markers, like CRP and other immune markers

Exploratory Endpoints: Baseline-to-week-6 changes in RSFC will be evaluated with resting-state functional magnetic resonance imaging (MRI) scans. Baseline-to-week-6 changes in BBB permeability will be evaluated with dynamic contrast enhanced MRI.

Safety endpoints: 1) treatment-related adverse events; 2) Columbia-Suicide Severity Rating Scale at each time point

Study Population: Up to n=20 adults (Aged 18-70 years; male and female) with a primary diagnosis of MDD who have failed two adequate trials of medication in the current depressive episode. Demographics reflective of the greater NYC population.

Phase: Phase 2 study

[figure not shown]
Description of Sites/Facilities Enrolling Participants: The human research will be conducted at the Icahn School of Medicine at Mount Sinai (ISMMS). Research will be conducted at the Depression and Anxiety Center for Discovery and Treatment, the Clinical Research Unit (CRU), the Infusion Suite of the Psychiatry Department of ISMMS. Functional MRI scans will be completed at the BioMedical Engineering and Imaging Institute (BMEII) in the Hess Center for Science and Medicine.

Description of Study Intervention: One treatment condition in an open-label study design: ixekizumab 160 mg (two 80 mg subcutaneous injections) at Week 0, followed by 80 mg at Weeks 2 and 4.

Study Duration: The proposed study is to be completed in 24 months.

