1.2 SCHEMA

1.3 SCHEDULE OF ACTIVITIES (SOA)

Study Phase	Screening	Open-label Treatment Period (Bi-Weekly Study Visits)			Primary Outcome	Study Exit
Study Visit	V0	V1	V2	V3	V4	V5
Week	-4 - 0	0	2	4	6	8
Screening						
Informed Consent	x					
Inclusion/Exclusion Criteria	x					
Demographics	x					
Medical History	x					
Family Psychiatric History	x					
ATRQ	x					
SCID-5-RV	x					
QIDS-C	x					
CGI-S	x					
Study drug administration						
Ixekizumab Treatment		x	x	x		
Safety assessments, concomitant medication and compliance monitoring						
Physical Exam	x				x	
Vital Signs	x	x	x	x	x	
Laboratory Tests	x				x	
U-Toxicology	x	x			x	
Pregnancy Test	x	x	x	x	x	
Adverse Events Monitoring	x	x	x	x	x	x
C-SSRS Past Month	x					
C-SSRS Since Last Visit		x	x	x	x	x
Clinical efficacy assessments						
MADRS		x	x	x	x	x
CGI-S	x	x	x	x	x	x
CGI-I		x	x	x	x	x
SHAPS		x	x	x	x	x
TEPS		x	x	x	x	x
QIDS-SR		x	x	x	x	x
HAM-A		x	x	x	x	x
Blood Markers						
Immune Markers		x			x	
Neuroimaging						
fMRI (RSFC)/DCE-MRI		x			x	
	* Study visits 1-5 may occur 3 days before or after the scheduled visit.					

	
* Clinical laboratory tests include chemistry, complete blood count, liver function tests, TB test, and thyroid-stimulating hormone levels (see protocol for details).
 
Abbreviations: ATRQ, Antidepressant Treatment Response Questionnaire; C-SSRS, Columbia-Suicide Severity Rating Scale; CGI-I, Clinical Global Impression-Improvement; CGI-S, Clinical Global Impression-Severity; fMRI, functional Magnetic Resonance Imaging; MADRS, Montgomery-Asberg Depression Rating Scale; QIDS-SR, Quick Inventory of Depressive Symptomatology-Self-Report; QIDS-C, Quick Inventory of Depressive Symptomatology-Clinician Rated; SHAPS, Snaith-Hamilton Pleasure Scale; TEPS, Temporal Experience of Pleasure Scale; HAM-A, Hamilton Anxiety Rating Scale

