The Quick Inventory of Depressive Symptomatology, Clinician Rated (QIDS-C): The QIDS-C²¹ is a 16-item instrument designed to assess the severity of depressive symptoms. The 16 items cover the nine symptom domains of major depression and are rated on a scale of 0-3. Total score ranges from 0 to 27, with ranges of 0-5 (normal), 6-10 (mild), 11-15 (moderate), 16-20 (moderate to severe), and 21+ (severe). This instrument will be used at the screening visit.

Clinical Global Impression - Severity (CGI-S): this is a widely administered clinician rated global measure of subject overall illness severity. Subjects are rated on a 1-7 scale where 1 corresponds to "Normal, Not at All Ill", 2 is "Borderline Mentally Ill", the anchor for 3 is "Mildly Ill", the anchor for 4 is "Moderately Ill", 5 is "Markedly Ill", 6 is "Severely Ill", and 7 is "Among the Most Extremely Ill Patients".

Clinical Global Impression - Improvement (CGI-I): this is a widely administered clinician rated global measure of the degree of improvement from the initial assessment in subject overall illness severity. Subjects are rated on a 1-7 scale where 1 corresponds to "Very Much Improved", 2 is "Much Improved", the anchor for 3 is "Minimally Improved", the anchor for 4 is "No Change", 5 is "Minimally Worse", 6 is "Much Worse", and 7 is "Very Much Worse".

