8.2 EVALUATIONS BY VISIT

SCREENING VISIT (V0, WEEK -4 – 0)

1. Review the study with the subject and obtain written informed consent and HIPAA authorization.
2. Review inclusion and exclusion criteria.
3. Assign the subject a unique screening number.
4. Record demographics data.
5. Record medical, psychiatric, family, medication and treatment history, diagnosis date, and prior treatments.
6. Record concomitant medications.
7. Perform self and clinician administered ratings scale:

- SCID-5-RV
- CGI-S
- CSSR-S – Past month
- QIDS-C

8. Perform a complete physical examination.
9. Perform and record vital signs.
10. Urine for urinalysis, urine toxicology and pregnancy test (female subjects who are of childbearing age).
11. Collect blood for clinical laboratory tests.
12. Schedule subject for Baseline (Visit 1) within 4 weeks of Screening.

Note: The screening visit may occur on up to three separate days. The whole procedures will be completed before the treatment day and within four weeks of the first screening visit. Screening measures may be completed under a separate screening protocol at each site. As long as the assessments are completed within four weeks of the signing of consent for this protocol, the screening measures will not be repeated. Subjects who are deemed screen fails may be re-screened at a later date, based on PI discretion. If re-screened, subjects will repeat all screening procedures.

A portion of this visit, including clinician administered rating scales, may be completed remotely via a HIPAA-compliant virtual platform.

BASELINE (V1, WEEK 0)

1. Obtain interval medical history.
2. Record any AEs.
3. Record changes to concomitant medications.
4. Collect urine for urine toxicology and pregnancy test (female subjects who are of childbearing age).
5. Record vital signs
6. Perform self and clinician administered ratings scale:
 - MADRS
 - CSSRS-Since Last Visit
 - HAM-A
 - CGI-S
 - CGI-I
 - SHAPS
 - TEPS
 - QIDS-SR
7. Neuroimaging procedures.
8. Collect blood immunological measures.
9. Dispense study medication.

Note: The Baseline Visit should take place within four-weeks of the date that the subject signed consent for this study. The Baseline Visit may occur on up to two separate days within 5 business days of each other. The neuroimaging procedures must be completed before the subject is randomized and receives

the study drug.

VISIT 2 (WEEK 2)

1. Obtain interval medical history.
2. Record vital signs
3. Record any AEs.

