9.4.3 ANALYSIS OF THE SECONDARY ENDPOINT(S)

1) Baseline-to-week-6 changes in depression severity, measured by MADRS scores

MADRS scores will be reported descriptively at each time point using the number observed, mean, standard deviation, median, and interquartile range. Individual patient trajectories will be plotted over time to explore patterns in treatment response. Mean change in MADRS scores from baseline and corresponding 95% confidence intervals will also be reported at each time point.

2) Response and remission rates at week 6

The number and proportion of patients who respond to treatment and who remain in remission will be reported at each time point.

3) Baseline-to-week 6 changes in other clinical symptoms as measured by CGI-S, CGI-I, QIDS-SR, C-SSRS, SHAPS, TEPS, and HAM-A.

4) Baseline-to-week-6 changes in RSFC as evaluated by fMRI scans and changes in BBB permeability

RSFC and BBB permeability will be analyzed in the same manner described above for MADRS scores.

5) Baseline-to-week-6 changes in blood-based immune markers, including CRP and other immune markers

Biomarkers will be analyzed in the same manner described for MADRS scores above.

6) the relationship between baseline-to-week-6 changes in blood-based immune markers and RSFC and BBB permeability with changes in depression severity scores.

We will explore whether improving depressive symptoms correlate with changes in blood-based immune markers and RSFC and BBB permeability. MADRS scores will be plotted with biomarkers, RSFC, and BBB over time to evaluate trends descriptively. Fixed and mixed effects regression models may also be explored to estimate associations and 95% confidence intervals.

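### The week-6 remission rule has no condition on the V1 MADRS, so a participant already at 10 or below before the first dose counts as a remitter with no change on ixekizumab

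*Combined protocol and SAP*

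**What the plan says.** **Entry.** Section 5.1, criterion 7 requires "Quick Inventory of Depressive Symptoms – Clinician Administered (QIDS-C) score ≥ 14". Section 8.1 says of the QIDS-C: "This instrument will be used at the screening visit". In the Schedule of Activities (section 1.3), the row "Inclusion/Exclusion Criteria" is marked at V0 only, and the MADRS row begins at V1. The MADRS has no minimum score anywhere. The CGI-S is rated at both visits without a cut-off.

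**Timing.** Section 8.2 instructs the site: "Schedule subject for Baseline (Visit 1) within 4 weeks of Screening". Its V1 list takes the MADRS, then neuroimaging, blood samples and study drug. The list contains no eligibility re-check and no step that depends on the V1 scores.

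**Endpoint.** Remission at week 6 is defined in sections 1.1 and 3 as "MADRS total score of ≤ 10", and response as a MADRS improvement of at least 50%. Section 9.4.3 item 2 adds: "The number and proportion of patients who respond to treatment and who remain in remission will be reported at each time point". Neither the definition nor the analysis text sets a condition on the V1 score.

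**The concern.** Depression scores move, and up to 4 weeks can separate the severity check from the first dose. The plan leaves room for improvement unrelated to the study drug in that window. Criterion 6 accepts an antidepressant dose that has been stable for just over 4 weeks, while section 8.1 says the ATRQ treats 6 weeks as an adequate trial. A participant can therefore reach V1 while a background antidepressant is still within its own trial period.

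A participant who has fallen to MADRS 10 or less by V1 and stays there adds to the week-6 remission count, although nothing changed after dosing. Sections 2.1 and 4.2 say the data will inform larger trials. In a single-arm study of up to 20 people no comparison group would absorb the error, so a reader would take the rate as remission reached on treatment.

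Section 9.4.3 item 2 makes this slightly worse. Because the MADRS is scheduled at V1, reporting remission at every time point, read literally, includes a remission figure taken before any drug.

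**Working it through.** **1. The plan's own figure.** The plan gives no expected remission rate. Its one precision figure is a 95% interval width of 0.35 for the completion proportion (section 9.2, n = 20, p = 0.8). The Wald formula reproduces it: 2 × 1.96 × √(0.8 × 0.2 / 20) = 0.351. Nothing below alters it.

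**2. The definitions applied to single cases** (baseline = V1, as section 8.2 labels it).

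| V1 MADRS | Week-6 MADRS | Change | Remitter (≤10) | Responder (≥50%) |
|---|---|---|---|---|
| 9 | 9 | 0 | yes | no (0%) |
| 12 | 6 | −6 | yes | yes (6/12 = 50%) |
| 20 | 10 | −10 | yes | yes (10/20 = 50%) |

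The first row is the defect. In the second and third rows all the change follows V1. A week-6 score of exactly 10 is also a response only if V1 was at least 20.

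**3. Effect of one case.** With all 20 in the denominator, one case adds 1/20 = 5 percentage points, two add 10 and three add 15.

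**4. How often it might happen.** The documents do not give the distribution of V1 MADRS, so these inputs are assumptions: QIDS-C mean 15, SD 4, selected at ≥14; V1 MADRS mean 28, SD 8 before selection; bivariate normal with correlation 0.6 to 0.4; mean improvement before dosing of 0, 3 or 6 points. Let p = P(V1 MADRS ≤10 | QIDS-C ≥14). Then P(at least one of 20) = 1 − (1 − p)^20, the expected number is 20p, and the expected addition to the remission rate is at most 100p percentage points, reached if all of them are still at 10 or less at week 6.

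| Assumed improvement before dosing | p | P(at least one of 20) | Expected number of 20 | Expected addition to rate, at most |
|---|---|---|---|---|
| 0 points | 0.001-0.004 | 2-8% | 0.02-0.08 | 0.1-0.4 points |
| 3 points | 0.005-0.012 | 9-22% | 0.09-0.24 | 0.5-1.2 points |
| 6 points | 0.015-0.032 | 26-48% | 0.30-0.64 | 1.5-3.2 points |

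The lower end of each range is correlation 0.6 and the upper end is 0.4. Example: p = 0.0319 gives 1 − 0.9681^20 = 0.48.

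**5. Without a distributional model.** If the share at 10 or less by V1 is simply assumed to be 2%, 5% or 10%, the chance of at least one in 20 is 1 − 0.98^20 = 33%, 1 − 0.95^20 = 64% or 1 − 0.90^20 = 88%. The two larger shares exceed anything in step 4, where the maximum is 3.2%.

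**The case against.** **Size.** Five points per case is conditional on a case occurring. Averaged over the assumed settings the addition is about 0.1 to 3 points. The documents do not support an average 6-point improvement before dosing: participants have had at least two adequate trials in the current episode, and any antidepressant dose must be stable. This stands. The case for the change is that the definition can return a wrong count, not that it often will.

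**Visibility.** Section 9.4.3 already plans MADRS summaries and individual trajectories, so a flat 9-to-9 line among 20 would be seen. A V1 remission count would also disclose such cases. This stands in part: a plot shows the participant but leaves the reported rate unchanged.

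**Status.** Section 9.1 calls the secondary endpoints exploratory, with no formal testing. This stands and limits the weight of the point.

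**Discretion.** Exclusion 15 and the best-interest wording in section 7.1 let the investigator act. Neither sets a severity value or a V1 check, so this is only a partial safeguard.

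**Stronger readings that the documents do not support.**
- A reader might infer that the response rate is also inflated by recovery before dosing. It is not: response is measured from the V1 score, so earlier improvement is excluded. A fall from 12 to 6 occurs wholly after V1.
- A reader might count everyone who starts with a mildly raised MADRS, for example below 20. The plan has no such cut-off, and scores of 11 to 19 are not remission.
- A reader might conclude that a MADRS entry check at V1 is required. The severity criterion is on the QIDS-C, which is not scheduled at V1, and no MADRS threshold exists. Selecting on the same V1 MADRS that serves as baseline would also add regression to the mean in a single-arm trial and, with open-label ratings, a reason to rate high at entry.
- A reader might put the gap between screening and V1 at about 8 weeks. Section 8.2 says of ratings made under a separate protocol, "As long as the assessments are completed within four weeks of the signing of consent for this protocol, the screening measures will not be repeated", and then, "The Baseline Visit should take place within four-weeks of the date that the subject signed consent for this study". The same section also requires all screening procedures within four weeks of the first screening visit. These sentences need reconciling, but the point here does not depend on the longer gap.

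**Conclusion.** The point holds for remission only. As written, the rule counts a participant who was at MADRS 10 or less before the first dose and is still there at week 6, which is not remission on ixekizumab. That follows from the definitions and needs no assumption.

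How often it would happen does rest on assumptions, because the documents give no V1 MADRS distribution: a 2-8% chance of at least one case in 20 with no improvement before dosing, rising to 26-48% if scores improve by an average of 6 points. One case moves the reported rate by 5 percentage points. The primary endpoint (receipt of all three doses), its interval and the response rate are not affected. Mean MADRS change would not count the earlier improvement either, though such a participant has little room left to improve. This is a modest but genuine fault in a descriptive secondary endpoint, worth correcting because the correction is free.

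**What to change.** In section 9.4.3 item 2, with the same definition carried into sections 1.1 and 3:

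1. Count remission only as MADRS above 10 at V1 and 10 or less at week 6.
2. Give the remission rate among participants with V1 MADRS above 10, and state that this denominator is a subset of the ITT population.
3. List separately, with V1 and week-6 scores, anyone already at 10 or less at V1.
4. Report response and remission by time point for post-dose visits only.

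**Cost.** This is analysis wording only, since the V1 MADRS is already collected. The remission rate may be slightly lower. As a hypothetical illustration, 6 remitters of 20 that include one participant already at 10 or less would change from 6/20 = 30% to 5/19 = 26%.

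**Limit.** A move from 11 to 10 would still count as remission on one point of change. The separate response figure and the planned individual trajectories show how much change lies behind each remission.

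Whether to re-confirm severity at V1, and on which scale, is a trade-off for the sponsor and is not part of this change.

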5.2 EXCLUSION CRITERIA

1. A primary psychiatric diagnosis other than MDD as defined by DSM-5; [comorbid anxiety disorders (including agoraphobia, generalized anxiety disorder, social anxiety disorder and panic disorder) and posttraumatic stress disorder (PTSD) are allowed];
2. Has a history of schizophrenia or other psychotic disorder, major depressive disorder with psychotic features, or bipolar I or II disorder;
3. Diagnosis of a major neurocognitive disorder;
4. Meets criteria for a moderate or severe substance use disorder within the past 6 months, with the exception of nicotine use disorder;
5. The patient is pregnant or breastfeeding;
6. Any contraindication to MRI or gadolinium including claustrophobia, any trauma or surgery which may have left magnetic material in the body, magnetic implants or pacemakers, inability to lie still for 1 hour or more, any known allergy to gadolinium;*
7. Positive urine toxicology screen for illicit drugs at the time of screening;
8. Serious and imminent risk of self-harm or violence as determined by the PI;
9. History of suicide attempt in the past 2 years or screening CSSRS Ideation Score >2 in the past month;
10. Clinically significant abnormalities of laboratory tests or physical examination;
11. Any unstable medical illnesses including hepatic, renal, gastroenterological, respiratory, cardiovascular (including ischemic heart disease); endocrinologic, neurologic (including history of severe head injury), immunologic, or hematologic disease;
12. Presence of TB as assessed by Quantiferon Gold test at screening;
13. Concomitant treatments with other biologics or other immune-suppressant agents; PRN use of NSAIDs is permissible;
14. Female participants who are pregnant, breastfeeding, or may become pregnant, or unwilling to practice birth control during participation in the study or the 6 months following;
15. Presence of a condition or abnormality that in the opinion of the Investigator would compromise the safety of the patient or the quality of the data.

